### **Imputation Approach if 10 Events or More are Observed**

In the case that 10 post-discharge events or more are observed in this group of discharged subjects, missing events will be imputed using PROC MI adjusting for baseline ordinal score as shown in the below pseudocode.

#### **Pseudocode:**

- DEFINE input2 as the analysis dataset containing all discharged subjects including those with missing event to be imputed and those with known outcome.

```
proc mi data=input2 out= imp_out2 n impute=20 seed = 748485 noint;
class baseordscorevar eventD29;
var eventD29;
monotone logistic(eventD29= baseordscorevar);
run;
```

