#### Pseudocode:

- DEFINE eventD29 as the binary variable for death or progression to mechanical ventilation or death by Day 29 (1=Yes, 0=No, .=Missing)
- DEFINE input1 as the full analysis dataset containing all baseline covariates and event indicator for complete data subjects as well as subjects with no post-baseline data with missing event indicator to be imputed.

- DEFINE imp\_out1 as the output dataset containing the 20 imputed datasets

```
proc mi data=input1  out= imp_out1 nimpute=20 seed = 837405 nointprint;
class trtvar baseordscorevar basedexausefl blackhispfl comorb2fl eventD29;
var trtvar baseordscorevar basedexausefl age blackhispfl comorb2fl basecrp eventD29;
monotone logistic(eventD29= trtvar baseordscorevar basedexausevar age blackhispfl
comorb2fl basecrp );
run;
```

The above procedure will output imp\_out1 dataset which contains 20 replicates for each subject. Update the dataset to remove subjects with complete data and only keep the 20 imputed datasets for subjects with no post-baseline data.

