##### Imputation Approach if Less than 10 Events are Observed

If, as expected, less than 10 post-discharge events are observed in the discharged group, missing incidence of mechanical ventilation or death data for these subjects will be imputed from a simple binomial distribution with the event rate calculated as the proportion of discharged subjects with known outcome (i.e., discharged to a location other than LTAC, hospice care or other hospital) who died or progressed to mechanical ventilation after discharge, without adjusting for any covariates in this group.

If no event is observed in a given analysis such as in subgroup analyses, the event rate of 0.5/total number of discharged subjects with outcome in the subgroup will be used instead of 0.

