##### Pseudocode:

- DEFINE eventD29 as the binary variable for death or progression to mechanical ventilation or death by Day 29 (1=Yes, 0=No, .=Missing)
- DEFINE input2 as the analysis dataset containing discharged subjects with missing event.
- Define evnrate as the event rate among subjects discharged to a location other than LTAC, hospice care or other hospital who have known outcome.
- DEFINE imp\_out2 as the output dataset containing the 20 imputed datasets

```
data imp_out2;
  set input2;
  subid=input(substr(usubjid,5,4),best12.);
  seed=3849+subid;
  call streaminit(seed);
  p=&evnrate;
  do i=1 to 20;
    _imputation_ = i;
    eventD29=rand("Binomial",p,1);
    output;
  end;
  drop p i;
run;
```

imp\_out2 contains 20 imputed values for each subject discharged to a location other than LTAC, hospice care or other hospital who had missing event.

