**Pseudocode:**

- DEFINE eventD29 as the binary variable for death or progression to mechanical ventilation or death by Day 29 (1=Yes, 0=No, .=Missing)
- DEFINE input3 as the analysis dataset containing subjects lost to follow-up while hospitalized or transferred with missing event. Add the variable for the probability of an event between last assessment and Day 29 (**pe**) calculated in step 3 to the dataset for subjects with missing data to be imputed.
- DEFINE imp\_out2 as the output dataset containing the 20 imputed datasets

```
data imp_out3;
  set input3;
  subid=input(substr(usubjid,5,4),best12.);
  seed=7564+subid;
  call streaminit(seed);
  p=&pe.;
  do i=1 to 20;
    _imputation_ = i;
    eventd29=rand("Binomial",p,1);
    output;
  end;
  drop p I ;
run;
```

imp\_out3 will have 20 imputed values for each subject who was lost to follow-up while hospitalized or transferred and had missing event.

Combine the 3 output datasets from the three different imputations.

```
data imp_out_all;
  set imp_out1 imp_out2 imp_out3;
run;
```

Create 20 replicates for each subject with non-missing event:

```
data complete_all;
  set complete;
  do i=1 to 20;
    _imputation_ = i;
    output;
  end;
  drop i;
run;
```

The final dataset to be used for analysis will be created by combined imputed data and complete data:

```
data imp_out;
  set imp_out_all complete;
  proc sort; by subject_imputation_;
run;
```

Using this imp\_out dataset, calculate odds ratio follow:

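### SAP 6.5.1.2: if the branch for 10 or more post-discharge events is triggered, known-outcome subjects are left in the imputation output, and the stacked primary-analysis dataset is wrong

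*SAP*

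**What the plan says.** Section 6.5.1.2 of the SAP imputes the Day 29 event for subjects lost to follow-up after discharge. It has two branches.

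- **Fewer than 10 post-discharge events.** This is the expected case: "If, as expected, less than 10 post-discharge events are observed in the discharged group". The input is limited to subjects who need imputing: "DEFINE input2 as the analysis dataset containing discharged subjects with missing event".
- **10 or more.** PROC MI is used instead, and the input is widened: "DEFINE input2 as the analysis dataset containing all discharged subjects including those with missing event to be imputed and those with known outcome". The pseudocode ends with the PROC MI call.

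Section 6.5.1.1 uses PROC MI in the same way for subjects with no post-baseline data. It describes the output as a dataset "which contains 20 replicates for each subject", and then gives a further instruction: "Update the dataset to remove subjects with complete data and only keep the 20 imputed datasets for subjects with no post-baseline data".

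The three outputs are combined at the end of Section 6.5.1.3 with "set imp_out1 imp_out2 imp_out3". A separate step follows: "Create 20 replicates for each subject with non-missing event". Its result is named `complete_all`. The last data step, however, reads "set imp_out_all complete".

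**The concern.** PROC MI needs the known outcomes in order to fit its model, so widening the input is reasonable. The known-outcome records must then be dropped from the output, because those subjects are added from their own dataset later. Section 6.5.1.1 does this; the branch for 10 or more events does not. A subject discharged with a known outcome therefore arrives from two sources.

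The combined file feeds the primary odds ratio and p-value (SAP 8.1.1) and the bootstrap risk difference (end of 6.5.1). Table 2 applies the same imputation to the third key secondary endpoint. Records counted twice are treated as independent information, so the model standard error is too small. Event-free subjects are the most likely to have been discharged, so they are over-weighted and the event rates fall.

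The same PROC MI call also lists only `eventD29` in its VAR statement, although the model line uses `baseordscorevar`. The call in 6.5.1.1 lists its covariates before the outcome.

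**Working it through.** **1. Tracing one subject through the code (branch for 10 or more events)**

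| Subject | From `imp_out2` | With `complete_all` stacked | With `complete` stacked, as printed |
|---|---|---|---|
| Discharged, outcome missing | once per imputation | once | once |
| Discharged, outcome known | once per imputation | **twice** | once |
| Not discharged, outcome known | none | once | **absent from all 20** |

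The last column arises because `complete` carries no `_imputation_` value. Its records form a separate BY group outside the 20 imputed datasets. Under that reading the expected branch would contain no known-outcome subject at all, so `complete` is evidently a slip for `complete_all`.

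**2. Planning figures (SAP 5)**

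The inputs are 400 subjects, taken as 200 per arm, a 16% control rate, an odds ratio of 2.5 and two-sided alpha .049.

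- Treated odds = (0.16/0.84)/2.5 = 0.0762, so the treated rate is 7.08%.
- Unpooled standard error = √(0.16×0.84/200 + 0.0708×0.9292/200) = 0.0316.
- Power = Φ(0.0892/0.0316 − 1.969) = 80.3%. The pooled form gives 79.7%.
- At a 21% control rate the two forms give 89.2% and 88.7%.

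The SAP's 80% and 89% are reproduced and are not in question.

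**3. One dataset at the planning rates**

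Events are 32/200 and 14/200. The standard error of the log odds ratio is √(1/a + 1/b + 1/c + 1/d).

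- Counted once: √(1/32 + 1/168 + 1/14 + 1/186) = 0.338. The odds ratio is 0.395, z = −2.75, and the risk difference is −9.0 points.
- Counted twice, assuming 10 post-discharge events split 7:3 and 95% of non-events discharged: the event cells become 39 and 17, and the non-event cells 168×1.95 = 327.6 and 186×1.95 = 362.7.
- The standard error is then √(1/39 + 1/327.6 + 1/17 + 1/362.7) = 0.300, which is 11% too small. The odds ratio is 0.394 and z = −3.10.
- The event rates become 39/366.6 = 10.6% and 17/379.7 = 4.5%, so the risk difference is −6.2 points.

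With 80-100% of non-events discharged, the standard error stays at 0.300-0.301 and the risk difference lies between −6.0 and −6.6 points.

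**4. Type I error if the branch fires and the double entry is run**

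The simulation has 200 per arm and a common event rate of 46/400 = 11.5%. It assumes 95% of non-events discharged, keeps only trials with at least 10 post-discharge events, and uses the unadjusted Wald test at .049. The chance of the branch firing is P(X ≥ 10), with X binomial (400, 0.115 × share).

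| Assumed share of events that are post-discharge | Chance of branch | Type I error, double entry | Type I error, single entry | Mean model SE (double) | True SD (double) |
|---|---|---|---|---|---|
| 10% | 2% | 9% | 4.5% | 0.27 | 0.32 |
| 15% | 16% | 9% | 4.6% | 0.27 | 0.33 |
| 25% | 71% | 10% | 4.6% | 0.27 | 0.33 |
| 40% | 99% | 12% | 4.7% | 0.27 | 0.34 |
| 60% | >99% | 14% | 4.7% | 0.25 | 0.34 |

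At a 5% share the branch fires in about 0.01% of trials.

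**The case against.** The strongest reply is that the intent is clear. These blocks are labelled pseudocode. Under the branch for fewer than 10 events, `imp_out2` is described as holding values only for subjects with a missing event. Section 6.5.1.1 states the removal rule, and the final file is described as imputed data plus complete data. A careful programmer would supply the line. That much stands: this is an omission in the code, not a decision to count subjects twice. But the SAP writes the removal out for one PROC MI step and omits it for the other, and the branch as printed gives a wrong file under either reading of the stacking line.

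The second reply is that the branch may never run. This also stands. The SAP expects fewer than 10 such events, and the expected branch has no duplication. The main sensitivity analysis (SAP 8.1.2) counts discharged subjects with missing outcomes as non-events, so it does not need this step.

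Three stronger readings are tempting, and the documents do not support them.

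- **That the primary analysis as planned carries a type I error of 9-14%.** This holds only if the branch fires and the double entry is run.
- **That the code exactly as printed enters subjects twice.** Run literally, it drops undischarged known-outcome subjects instead.
- **That at least 22% of events must be post-discharge for the branch to matter.** The ratio 10/46 = 22% is the share at which 10 events are expected, not a minimum. The branch can fire at lower shares.

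**Conclusion.** The point holds as a defect in a contingent branch. If 10 or more post-discharge events occur, the printed steps do not give one record per subject per imputation. With the evident correction to `complete_all`, type I error is about 9-10% for post-discharge shares of 10-25%, and 12-14% for assumed shares of 40-60%, against a nominal 4.9%. At the planning rates with 10 such events, the standard error is about 11% too small, the odds ratio is almost unchanged, and the arm event rates and risk difference are understated.

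These sizes rest on an unadjusted two-by-two analysis, not the four-covariate model with pooled imputations. They also rest on assumed discharge shares. The nearest figure in the documents is about 75% discharged by Day 8 in LIVE-AIR (Protocol 1.1.1). No document gives the post-discharge share of events, so the chance of the branch firing is unknown. The full ITT set contains the primary subgroup, so its count of such events cannot be lower, but how much higher cannot be said.

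The correction should be made because a pre-specified fallback in a confirmatory analysis has to work when it is called.

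**What to change.** - In 6.5.1.2, after PROC MI in the branch for 10 or more events, keep only subjects whose `eventD29` was missing in `input2`, as 6.5.1.1 does for its own step.
- In the same call, list `baseordscorevar` before `eventD29` in the VAR statement.
- In the last data step of 6.5.1.3, stack `complete_all` instead of `complete`.
- Add a check that each of the 20 datasets has exactly one record per subject in the analysis set.

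The cost is a few lines of SAP code. It needs no new data and does not change the planned method.

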#### **6.5.1.3. Imputation Strategy for Subjects Lost to Follow-up while Hospitalized or Transferred**

This group includes subjects with post-baseline data available who were lost to follow-up or terminated early from the study prior to Day 29 and prior to death or progression to mechanical ventilation and were still hospitalized or discharged to LTAC, hospice care or other hospital at the time of their last assessment. Missing incidence of mechanical ventilation or death data for these subjects will be imputed using the algorithm described below that takes into account each subject's baseline covariates and time of last assessment. For each of these subjects with missing event, the first step will be to estimate the probability of having an event between their last assessment date and Day 29 which will be estimated from a Cox model as described below:

**Step 1:** Define a dataset including all subjects regardless of missingness except those that have no post baseline data. For all subjects who terminated early without event, consider them as non-events and censor them at the time of last assessment.

**Step 2:** Fit a Cox proportional hazards model for all subjects in step 1 using the following covariates: randomized treatment group (trtvar), baseline dexamethasone use (basedexavar), baseline actual ordinal score (baseordscorevar), age, indicator for black or Hispanic ethnicity (blackhispfl), presence of 2 or more comorbidities(comorb2fl), and baseline CRP (basecrp). The resulting Cox proportional hazards model will be of this form:

$$h(t) = h_0(t) \exp(b_1X_1 + b_2X_2 + \dots + b_pX_p)$$

where

$h(t)$ : Expected hazard at time t.

$h_0(t)$ : Baseline hazard function and represent the hazard when all the covariates are zero.

$X_1, X_2, \dots, X_p$  : Covariates in the cox model

$b_1, b_2, \dots, b_p$  : Model coefficients.

#### **Pseudocode:**

- aval: time variable. All subjects except those with no post-baseline data are included. Subjects missing endpoint are censored at their last assessment day in this cox model.
- cnsr: Event indicator variable (1=No event, 0=event). Subjects with missing outcome are censored.
- Subjects\_miss: Dataset with subjects lost to follow-up while discharged or transferred whose endpoint needs to be imputed.
- Outset: Output dataset containing survival estimates for all subjects in subject\_miss dataset given their covariates for all timepoints specified in timelist.

```
proc phreg data = analysis;
class trtvar (ref = "Placebo + RDV") basedexavar(ref="No"); baseordscorevar (ref="5")
blackhispf1(ref="No") comorb2f1(ref="No");
model aval * cnsr(1) = trtvar basedexavar baseordscorevar blackhispf1 comorb2f1 basecrp
age / ties=efron;
baseline out = outset survival = survival covariates=subjects_miss timelist=1 to 29 by 1
/ method = emp;
run;
```

**Step 3:** For each subject to be imputed (i.e., those lost to follow-up while hospitalized/transferred), estimate the survival probability at their last assessment (SL) and the survival probability at Day 29 (S29). Then, the probability that this subject will have an event between their last assessment day and Day 29 is given by:

**Pe = Prob (Event by Day 29|no event through last assessment) = 1 – S29/SL**

**Step 4:** For each subject lost to follow-up while discharged or transferred to another hospital, impute the event from a binomial distribution using the event probability calculated in Step 3.

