#### 6.5.1.2. Imputation Strategy for Subjects Lost to Follow-up while Discharged

This group includes subjects with post-baseline data available who were lost to follow-up or terminated early from the study prior to Day 29 and prior to death or progression to mechanical ventilation and were discharged to a location other than LTAC, hospice care or other hospital at the time of their last assessment.

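### SAP 6.5.1.3 contradicts itself on which lost subjects get a Cox-based imputed outcome; two operative lines, read literally, leave out those lost while still in hospital

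*SAP*

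**What the plan says.** SAP 6.5.1 sorts subjects with a missing outcome into three groups, each with its own imputation model: no post-baseline data (6.5.1.1), lost after discharge (6.5.1.2), and lost in hospital or after transfer (6.5.1.3).

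The discharged group in 6.5.1.2 is those who "were discharged to a location other than LTAC, hospice care or other hospital at the time of their last assessment". The group in 6.5.1.3 is the complement, those who "were still hospitalized or discharged to LTAC, hospice care or other hospital at the time of their last assessment".

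Within 6.5.1.3 a Cox model is fitted, and its BASELINE statement scores the dataset `Subjects_miss`. Step 3 turns the survival estimates into Pe = 1 − S29/SL. Step 4 draws the outcome from a binomial distribution. Two of these lines name a group that is not the section's own:

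- `Subjects_miss`: "Dataset with subjects lost to follow-up while discharged or transferred whose endpoint needs to be imputed".
- Step 4: "For each subject lost to follow-up while discharged or transferred to another hospital, impute the event from a binomial distribution".

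**The concern.** The two lines are operative. `Subjects_miss` is the covariates dataset of the PHREG BASELINE statement, so the output holds survival estimates only for the subjects in it. Step 4 says who receives the draw. Neither names a subject who withdrew while still in the study hospital. A generous reading, in which discharge here means discharge to long-term acute care or hospice, does not bring that subject back.

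A subject without an imputed outcome does not enter the logistic model. SAP 6.3 bases the primary analysis on everyone randomized, and SAP 6.5 commits to multiple imputation for losses in hospital, so a literal program would break both rules. The algorithm feeds the primary analysis (8.1.1), the main sensitivity analysis (8.1.2), the second TMLE approach (6.5.2) and, through Table 2, the third key secondary endpoint.

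A related line needs the same care. The text before the draw code says the probability is added to `input3` as a variable, hence one value per subject. The code reads `p=&pe.`, the same macro form that 6.5.1.2 uses for its single common event rate.

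**Working it through.** **1. The lines side by side (SAP 6.5.1.3 unless noted)**

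- Heading, hospitalized or transferred: "Imputation Strategy for Subjects Lost to Follow-up while Hospitalized or Transferred".
- Opening definition: the same group (quoted above).
- `Subjects_miss`: discharged or transferred.
- Step 3, hospitalized or transferred: "For each subject to be imputed (i.e., those lost to follow-up while hospitalized/transferred".
- Step 4: discharged or transferred.
- Draw dataset, hospitalized or transferred: "DEFINE input3 as the analysis dataset containing subjects lost to follow-up while hospitalized or transferred with missing event".
- Draw output, hospitalized or transferred: "imp\_out3 will have 20 imputed values for each subject who was lost to follow-up while hospitalized or transferred and had missing event".
- SAP 6.5.2 (second approach) and Table 4 footnote g: hospitalized or transferred.

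Two lines disagree with all the others.

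**2. What each reading produces**

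The SAP gives no loss counts, so these are assumed. With N = 400, let d, h, t and b be the numbers lost after ordinary discharge, in hospital, after transfer, and with no post-baseline data. Complete cases are 400 − d − h − t − b. For d/h/t/b = 8/4/2/2 there are 384 complete cases.

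- A, hospitalized or transferred throughout: 384 + 2 + 8 + (4 + 2) = 400 records, one per subject.
- B, the stray wording applied everywhere, overriding Step 3 and `input3`: 384 + 2 + 8 + (8 + 2) = 404 records, with 8 subjects duplicated and 4 without an outcome.
- C, `Subjects_miss` literal, `input3` as defined: 4 in-hospital losses have no SL or S29, hence no Pe; 396 usable, no duplicates.
- D, Step 3 as written, Step 4 literal: in-hospital losses have a Pe but no draw, and discharged subjects have no Pe; 384 + 2 + 8 + 2 = 396 records, no duplicates.

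With 4/2/1/1 the figures for A, B, C and D are 400, 402, 398 and 398. With 16/8/4/2 they are 400, 408, 392 and 392. In-hospital losses go missing under B, C and D. Duplication occurs only under B.

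**3. Size: power**

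Inputs from SAP section 5: 400 subjects, OR 2.5, two-sided alpha .049. I assume 200 per arm. At a 16% control rate the treated odds are (0.16/0.84)/2.5 = 0.0762, so the treated rate is 7.08%. A pooled two-proportion test gives 79.7% (stated: 80%). At 21% the treated rate is 9.61% and power is 88.7% (stated: 89%). The plan's figures reproduce.

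Dropping h = 2, 4 or 8 subjects, split equally (199, 198 or 196 per arm), gives 79.5%, 79.3% and 78.9% at the 16% rate.

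**4. Size: bias, illustrative and unadjusted**

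Take h = 8 and a 40% event probability for these subjects, the top of the SAP's tipping-point grid (8.1.3). That is an assumption, not an expectation. Suppose the analysis that drops them gives OR 2.5 (placebo over lenzilumab). With them included:

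- All 8 on lenzilumab: (192 × 0.0708 + 8 × 0.40)/200 = 8.40%, and OR = 0.1905/0.0917 = 2.08.
- All 8 on placebo: (192 × 0.16 + 8 × 0.40)/200 = 16.96%, and OR = 0.2042/0.0762 = 2.68.
- Four per arm, with 40% on placebo and 21.1% on lenzilumab (the same OR of 2.5): rates 16.48% and 7.36%, and OR = 2.48.

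Balanced losses hardly matter. Clustered losses can move the estimate either way.

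**The case against.** The strongest reply is that the intent is plain. Apart from the two phrases, every statement of the group in 6.5.1.3 agrees, as do the cross-references, and the three-group scheme only works on that reading. A programmer would probably meet the contradiction at Step 3 rather than drop subjects silently. The tipping-point analysis and the first TMLE approach do not use these lines, and SAP section 5 expects little missing data. This stands, and it is why the point is a drafting error with a probably small effect. It does not remove the point, because the primary imputation algorithm should not leave a programmer to choose between conflicting populations.

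A reader might infer that subjects lost after ordinary discharge are imputed twice. The documents do not support that. The draw code reads `input3`, which is limited to hospitalized or transferred subjects, and Step 3 limits Pe to the same group. Duplication needs the stray wording to override both, so it is only a conditional risk. A reader might also infer that the plan departs from ITT or lowers the event rate. The plan as a whole intends to impute these subjects, and no loss counts exist from which to derive a direction.

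On `p=&pe.`, the block is labelled pseudocode and a macro reference can resolve to a variable name, so one common probability for everyone is not established. The code and the prose should still be made to match.

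**Conclusion.** The inconsistency is real and sits in lines that decide who is scored and who is drawn. Followed literally, either line leaves subjects lost while still in the study hospital without an imputed primary outcome. Context shows the intended group, so the finding is that the text needs correcting, not that the planned analysis omits or duplicates subjects.

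The size cannot be fixed from the documents. Under the assumed losses of 2 to 8 in-hospital subjects among 400, power falls by less than one percentage point. The odds ratio barely moves if the losses are balanced, and could move materially in either direction if they cluster in one arm. These figures rest on 1:1 allocation, the assumed loss counts and, for the bias illustration, the 40% event probability. The correction should be made before the primary analysis is programmed.

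**What to change.** 1. In the `Subjects_miss` definition and in Step 4, name the group given in the section's opening definition: still in hospital, or sent to long-term acute care, hospice or another hospital.
2. State that subjects lost after any other discharge are handled only in 6.5.1.2 and are excluded from `Subjects_miss` and `input3`.
3. Replace `p=&pe.` with `p=pe`, so that each subject's own probability from Step 3 drives the draw, as the prose already says.
4. Add a check that each subject appears exactly once for each `_imputation_` value, with a non-missing outcome. The same check would show that the final stacking step reads `complete` rather than the 20-fold `complete_all` created just before it.

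The cost is two phrases, one added sentence, one line of pseudocode and one programmed check. No sample size, alpha or estimand changes.
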